8.2.2. Exclusion Criteria

Patients meeting any of the following criteria will not be included in the study:

1. Patients participating in any interventional clinical trial.
2. Patients on active treatment for malignancies other than metastatic/locally advanced BC at the time of enrollment.
3. Patients who are unable to understand the nature of the study and are unwilling to sign an informed consent.

8.3. Variables

Patient demographics, clinical characteristics, comorbid conditions and concomitant medications, early/locally advanced and metastatic BC treatment history, current BC treatment, performance status (ECOG), clinical outcomes, laboratory/other investigations and QoL will be collected. Detailed definitions of variables and the Data Entry Schedule is provided in Table 1 and [Table 2](#).

Table 1. Study Variables

Variable	Operational Definition	Data Source(s)
Demographics	Age, ethnicity, weight, family history of BC (breast cancer (BRCA) gene testing performed).	Patient records
Clinical characteristics	Time since diagnosis, staging, node status, menopause status, diagnosis for which palbociclib combination was prescribed, sites of metastases, de novo versus recurrent disease.	Patient records

Variable	Operational Definition	Data Source(s)
Comorbid conditions and concomitant medications	Comorbid conditions and concomitant medications.	Patient records
Early or locally advanced BC treatment history	Adjuvant treatments received for early or locally advanced BC (Stages 0-IIIa). Time since end of adjuvant treatment. Surgery/radiotherapy received.	Patient records
MBC treatment history	Treatments and supportive therapies received since metastatic HR+/HER2- diagnosis. Duration of treatments.	Patient records
Current BC treatment	Starting dose, duration of treatment, changes in dose, interruptions, cycle delays and discontinuations. Line of treatment.	Patient records
Performance status (ECOG)	Eastern Cooperative Oncology group score.	Patient records
Clinical outcomes	
 Proportion of progression free survival/time to progression (at intervals per standard of care). Proportion of objective response rate (at intervals per standard of care). Complete response defined as complete reduction of all visible disease; partial response defined as partial reduction in size of visible disease in some or all areas without any areas of increase in visible disease; stable disease defined as no change in overall size of visible disease, also including cases where some lesions increased in size and some lesions decreased in size; progressive disease defined as an increase in visible disease and/or presence of any new lesions, including cases where the clinician indicates progressive disease. Time to response (at intervals per standard of care), defined as the time to first response among patients who achieved complete response or partial response. Proportion of overall survival (1- and 2-years post-treatment initiation). 	Patient records

Variable	Operational Definition	Data Source(s)
All lab investigations + other investigations	
 All lab investigation conducted including complete blood count (CBC). 	Patient records
Quality of life	
 To be assessed via EORTC QLQ-C30 (Cancer Quality of Life Questionnaire). 	Patient questionnaire

BC = breast cancer; CBC = complete blood count; ECOG = Eastern Cooperative Oncology Group; EORTC QLQ-C30 = European Organization for the Research and Treatment of Cancer Quality of Life Questionnaire Core 30; MBC = metastatic breast cancer.

Table 2. Data Entry Schedule

Data Collection and Entry ¹ ►	Baseline	During Treatment with Palbociclib	Post Treatment with Palbociclib
	SOC Visit ¹	SOC Follow-up visits ² through End of Treatment with Palbociclib	SOC Follow-up Visits through End of Study ³
Informed Consent & Inclusion/Exclusion Criteria	x		
Patient Demographics, Medical History, Baseline Metastatic Disease Status	x		
BC Diagnosis and Recurrence History	x		
Comorbid conditions	x	x	
Concomitant Medications	x	x	
BC Treatment ⁴	x	x	x ⁵
Performance Status (ECOG)	x	x	
Clinical Outcomes ⁶	x	x	
Laboratory investigations, including CBC ⁷	x	x	
EORTC QLQ-C30 ⁸	x	x	

BC = breast cancer; SOC = standard of care; CBC = complete blood count; ECOG = Eastern Cooperative Oncology Group; EORTC QLQ-C30 = European Organization for the Research and Treatment of Cancer Quality of Life Questionnaire Core 30.

1. Data is collected in accordance with normal standard of care visits; enter all data available per Data Entry Schedule into the electronic data capture system.
2. For a visit to be considered a follow-up visit, clinical outcomes data must be collected at minimum, in accordance with SOC.
3. Follow-up through End of Study: Enter data at SOC visits post palbociclib treatment.
4. BC treatment: including surgery, radiation, systemic chemotherapy, hormone therapy, and/or targeted therapy, in both neoadjuvant/adjuvant and metastatic disease settings, prior to, during and after palbociclib treatment; supportive care is also collected in the metastatic setting.
5. Data on the first immediate subsequent treatment used after the end of palbociclib treatment should be collected.
6. Clinical outcomes: overall clinical response as judged by treating physician, at intervals per standard of care schedule: progression free survival/time to progression, objective response rate, time to response and overall survival.
7. CBC: Baseline and during palbociclib treatment, enter any CBC during the 1st 3 cycles, then enter Day 1 (or prior to start of a new cycle) CBC for the subsequent cycles as per standard of care.
8. EORTC QLQ-C30 will be collected at baseline (before starting palbociclib) then every 3 months \pm 2 weeks after initiating treatment with palbociclib for the first year of treatment. After the first year of treatment with palbociclib, EORTC QLQ-C30 will be collected every 6 months \pm 4 weeks until the end of treatment with palbociclib.

PFIZER CONFIDENTIAL

CT24-WI-GL02-RF01 3.0 Non-Interventional Study Protocol Template For Primary Data Collection Study

02-Nov-2020

Page 19 of 41

090177e19bc3ff14\Approved\Approved On: 10-Nov-2022 09:28 (GMT)

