8. RESEARCH METHODS

8.1. Study Design

This is a prospective, non-interventional (NI), multicenter study being conducted in Africa Middle East (AfME) countries. The aim is to understand palbociclib treatment patterns, clinical outcomes and QoL for patients with metastatic/locally advanced BC being treated in routine clinical practice in 7 AfME countries: Egypt, Jordan, KSA, Lebanon, Morocco, Qatar and UAE.

Approximately 200 patients from 19 centers across the 7 countries will be enrolled. The recruitment period (ie, from first patient into last patient in) will span over 18 months.

[figure not shown]
Patients will be enrolled at the time of treatment initiation with palbociclib and will be followed up over a 24-month period at time intervals per routine care, or until patient's withdrawal from the study or death (whichever comes first). Prospective data on clinical characteristics, treatment patterns, clinical outcomes and QoL will be collected ([Figure 1](#)).

Participation in this study is not intended to change the routine treatment patients receive, as determined by their prescribing physicians; all treatment decisions, type and timing of the disease monitoring are per routine clinical care, and at the discretion of treating physician and patient.

All assessments described in this protocol are performed as part of normal clinical practice or standard practice guidelines for the patient population and healthcare provider specialty in the countries where this non-interventional study is being conducted.

All assessments described in this protocol are performed as part of normal clinical practice or standard practice guidelines for the patient population and healthcare provider specialty in the countries where this non-interventional study is being conducted.

Figure 1. Study Design

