8.4.2. Patient Questionnaires and Quality of Life

All patients enrolled in the study will be asked to participate in completing the Quality of Life Questionnaire, EORTC QLQ-C30, to be collected at baseline (before starting palbociclib) then every 3 months \pm 2 weeks after initiating treatment with palbociclib, for the first year of treatment, in accordance with routine standard of care visits. After the first year of treatment with palbociclib, EORTC QLQ-C30 will be collected every 6 months \pm 4 weeks until the end of treatment with palbociclib, in accordance with routine standard of care visits.

Patients will complete these questionnaires on a paper form.

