2.1.4. Patient Questionnaires and Quality of Life

All patients enrolled in the study will be asked to participate in completing the Quality of Life Questionnaire, EORTC QLQ-C30, to be collected at baseline (before starting palbociclib) then every 3 months ± 2 weeks after initiating treatment with palbociclib, for the first year of treatment, in accordance with routine standard of care visits. After the first year of treatment with palbociclib, EORTC QLQ-C30 will be collected every 6 months ± 4 weeks until the end of treatment with palbociclib, in accordance with routine standard of care visits.

Patients will complete these questionnaires on a paper form.

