3. ANALYSIS SETS/POPULATIONS

3.1. Full Analysis Set

The Full Analysis Set will contain all patients who fulfil the eligibility criteria. Date of enrollment is the date of Palbociclib treatment initiation (baseline).

Censoring rules: The maximum follow-up of a patient is 24 months. Patients will be censored at the end of Palbociclib treatment, or if the treatment continues, at 24 months. Other censoring events before 24 months are patient's withdrawal, disease progression or death, whichever occurs first. Patients' subsequent treatments after Palbociclib treatment discontinuation /disease progression will be recorded. Patients who are lost to follow-up will be censored at their last visit. For some clinical outcomes, different censoring rules will be applied as described in [Section 6.1](#), [Section 6.2](#), and [Section 6.3](#).

Data collection is estimated to start in Q2 2021 and it will end in Q4 2024.

Table and Figure Shells are presented in [ANNEX 2](#).

Patient inclusion and exclusion criteria are explained in [Section 2.1](#). Summary of patient enrolment per country and study site will be described as shown in [Table Shell 1](#).

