Quality of life of the patients receiving Palbociclib treatment at different follow-up visits will be described as shown in [Table Shell 47](#). The stratified tables will be presented as in [Table Shells 48-53](#). The EORTC quality of life questionnaire (QLQ-C30) will be used according to CRF. EORTC QLQ-30 scoring manual (version 3.0) will be used to group the items of the questionnaire into five functional scales, nine symptom scales, and a global health status, and to calculate scores for them. All of the scales and single-item measures range from 0 to 100;

a higher score represents a higher (“better”) level of functioning, or a higher (“worse”) level of symptoms. The procedure for scoring the scales is the same for all classes:

1. Estimate the average of the items that contribute to the scale; this is the raw scale.
2. Use a linear transformation to standardise the raw score so that scores range from 0 to 100.

Coding for SAS is provided in the appendix of EORTC QLQ-30 scoring manual.³⁵

Subgroup analyses will be performed as described in [Section 3.2](#).

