-MBC hormonal therapy (other than Palbociclib combination)	XX (xx%)	XX (xx%)
Radiotherapy	XX (xx%)	XX (xx%)
Surgery	XX (xx%)	XX (xx%)
Other	XX (xx%)	XX (xx%)
Unknown	XX (xx%)	XX (xx%)
Missing	XX (xx%)	XX (xx%)
Duration of therapy (days)		
Mean (SD)	xx.x (xx.x)	xx.x (xx.x)
Q1, median, Q3	xx.x, xx.x, xx.x	xx.x, xx.x, xx.x
Min, max	xx.x, xx.x	xx.x, xx.x
Missing	XX (xx%)	XX (xx%)

Table Shell 45 - Descriptive summary table of therapies of the advanced/metastatic BC patients (stages IIIb-IV) by age group *before* Palbociclib treatment.

Variable	Age		
	<55 years	55-64 years	≥65 years
Number of patients who received adjuvant therapies before Palbociclib treatment	XX	XX	XX
Systemic therapy	XX (xx%)	XX (xx%)	XX (xx%)
-MBC chemotherapy	XX (xx%)	XX (xx%)	XX (xx%)
-MBC hormonal therapy (other than Palbociclib combination)	XX (xx%)	XX (xx%)	XX (xx%)
Radiotherapy	XX (xx%)	XX (xx%)	XX (xx%)
Surgery	XX (xx%)	XX (xx%)	XX (xx%)
Other	XX (xx%)	XX (xx%)	XX (xx%)
Unknown	XX (xx%)	XX (xx%)	XX (xx%)
Missing	XX (xx%)	XX (xx%)	XX (xx%)
Duration of therapy (days)			
Mean (SD)	xx.x (xx.x)	xx.x (xx.x)	xx.x (xx.x)
Q1, median, Q3	xx.x, xx.x, xx.x	xx.x, xx.x, xx.x	xx.x, xx.x, xx.x
Min, max	xx.x, xx.x	xx.x, xx.x	xx.x, xx.x
Missing	XX (xx%)	XX (xx%)	XX (xx%)

0901776099673e30A5481150-Palbociclib On: 28-Feb-2023 09:56 (GMT)

Table Shell 46 - Descriptive summary table of quality of life of the patients receiving Palbociclib combination treatment.

	12 months	18 months	24 months	30 months	36 months
Total number of patients	Xx	Xx	Xx	Xx	Xx
Global health status					
[score]					
N	XX (xx%)	XX (xx%)	XX (xx%)	XX (xx%)	XX (xx%)
Mean (SD)	xx.x (xx.x)	xx.x (xx.x)	xx.x (xx.x)	xx.x (xx.x)	xx.x (xx.x)
Q1, median, Q3	xx.x, xx.x, xx.x	xx.x, xx.x, xx.x	xx.x, xx.x, xx.x	xx.x, xx.x, xx.x	xx.x, xx.x, xx.x
Min, max	xx.x, xx.x	xx.x, xx.x	xx.x, xx.x	xx.x, xx.x	xx.x, xx.x
Missing	XX (xx%)	XX (xx%)	XX (xx%)	XX (xx%)	XX (xx%)
Functional scales					
Physical functioning					
[score]					
N	XX (xx%)	XX (xx%)	XX (xx%)	XX (xx%)	XX (xx%)
Mean (SD)	xx.x (xx.x)	xx.x (xx.x)	xx.x (xx.x)	xx.x (xx.x)	xx.x (xx.x)
Q1, median, Q3	xx.x, xx.x, xx.x	xx.x, xx.x, xx.x	xx.x, xx.x, xx.x	xx.x, xx.x, xx.x	xx.x, xx.x, xx.x
Min, max	xx.x, xx.x	xx.x, xx.x	xx.x, xx.x	xx.x, xx.x	xx.x, xx.x
Missing	XX (xx%)	XX (xx%)	XX (xx%)	XX (xx%)	XX (xx%)
Role functioning					
[score]					
N	XX (xx%)	XX (xx%)	XX (xx%)	XX (xx%)	XX (xx%)
Mean (SD)	xx.x (xx.x)	xx.x (xx.x)	xx.x (xx.x)	xx.x (xx.x)	xx.x (xx.x)

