Q1, median, Q3	XX.X, XX.X, XX.X	XX.X, XX.X, XX.X	XX.X, XX.X, XX.X	XX.X, XX.X, XX.X	XX.X, XX.X, XX.X
Min, max	XX.X, XX.X	XX.X, XX.X	XX.X, XX.X	XX.X, XX.X	XX.X, XX.X
Missing	XX (xx%)	XX (xx%)	XX (xx%)	XX (xx%)	XX (xx%)
Financial difficulties [score]					
N	XX (xx%)	XX (xx%)	XX (xx%)	XX (xx%)	XX (xx%)
Mean (SD)	XX.X (XX.X)	XX.X (XX.X)	XX.X (XX.X)	XX.X (XX.X)	XX.X (XX.X)
Q1, median, Q3	XX.X, XX.X, XX.X	XX.X, XX.X, XX.X	XX.X, XX.X, XX.X	XX.X, XX.X, XX.X	XX.X, XX.X, XX.X
Min, max	XX.X, XX.X	XX.X, XX.X	XX.X, XX.X	XX.X, XX.X	XX.X, XX.X
Missing	XX (xx%)	XX (xx%)	XX (xx%)	XX (xx%)	XX (xx%)

The same format will be used to:

Table Shell 47.2 - Descriptive summary table of quality of life of the patients receiving Palbociclib combination treatment by combination. Palbociclib plus fulvestrant.

Table Shell 48.1 - Descriptive summary table of quality of life of the patients receiving Palbociclib combination treatment by line of treatment. First line.

	1st				
	12 months	18 months	24 months	30 months	36 months
Total number of patients	Xx	Xx	Xx	Xx	Xx
Global health status					
[score]					
N	XX (xx%)	XX (xx%)	XX (xx%)	XX (xx%)	XX (xx%)
Mean (SD)	xx.x (xx.x)	xx.x (xx.x)	xx.x (xx.x)	xx.x (xx.x)	xx.x (xx.x)
Q1, median, Q3	xx.x, xx.x, xx.x	xx.x, xx.x, xx.x	xx.x, xx.x, xx.x	xx.x, xx.x, xx.x	xx.x, xx.x, xx.x
Min, max	xx.x, xx.x	xx.x, xx.x	xx.x, xx.x	xx.x, xx.x	xx.x, xx.x
Missing	XX (xx%)	XX (xx%)	XX (xx%)	XX (xx%)	XX (xx%)
Functional scales					
Physical functioning					
[score]					
N	XX (xx%)	XX (xx%)	XX (xx%)	XX (xx%)	XX (xx%)
Mean (SD)	xx.x (xx.x)	xx.x (xx.x)	xx.x (xx.x)	xx.x (xx.x)	xx.x (xx.x)
Q1, median, Q3	xx.x, xx.x, xx.x	xx.x, xx.x, xx.x	xx.x, xx.x, xx.x	xx.x, xx.x, xx.x	xx.x, xx.x, xx.x
Min, max	xx.x, xx.x	xx.x, xx.x	xx.x, xx.x	xx.x, xx.x	xx.x, xx.x
Missing	XX (xx%)	XX (xx%)	XX (xx%)	XX (xx%)	XX (xx%)
Role functioning					
[score]					
N	XX (xx%)	XX (xx%)	XX (xx%)	XX (xx%)	XX (xx%)
Mean (SD)	xx.x (xx.x)	xx.x (xx.x)	xx.x (xx.x)	xx.x (xx.x)	xx.x (xx.x)
Q1, median, Q3	xx.x, xx.x, xx.x	xx.x, xx.x, xx.x	xx.x, xx.x, xx.x	xx.x, xx.x, xx.x	xx.x, xx.x, xx.x
Min, max	xx.x, xx.x	xx.x, xx.x	xx.x, xx.x	xx.x, xx.x	xx.x, xx.x
Missing	XX (xx%)	XX (xx%)	XX (xx%)	XX (xx%)	XX (xx%)
Emotional functioning					
[score]					
N	XX (xx%)	XX (xx%)	XX (xx%)	XX (xx%)	XX (xx%)
Mean (SD)	xx.x (xx.x)	xx.x (xx.x)	xx.x (xx.x)	xx.x (xx.x)	xx.x (xx.x)
Q1, median, Q3	xx.x, xx.x, xx.x	xx.x, xx.x, xx.x	xx.x, xx.x, xx.x	xx.x, xx.x, xx.x	xx.x, xx.x, xx.x

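### The SAP's quality-of-life tables have columns for months 12 to 36, but QLQ-C30 is collected from baseline to month 24, so four of seven scheduled assessments have no column and two columns can never be filled

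*Protocol*

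**What the plan says.** **Collection.** Protocol 8.3 (Table 2, footnote 8) states that "EORTC QLQ-C30 will be collected at baseline (before starting palbociclib) then every 3 months", with a window of 2 weeks either side, for the first year of treatment. Protocol 8.4.2 continues: "After the first year of treatment with palbociclib, EORTC QLQ-C30 will be collected every 6 months", with a window of 4 weeks either side, until palbociclib ends. SAP 2.1.4 repeats the schedule, with the form "to be collected at baseline (before starting palbociclib) then every 3 months" in year one and 6-monthly after that.

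**Follow-up.** Protocol 8.1 says that patients "will be followed up over a 24-month period at time intervals per routine care". SAP 3.1 is explicit: "The maximum follow-up of a patient is 24 months".

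**Reporting.** SAP 6.2 states: "Quality of life of the patients receiving Palbociclib treatment at different follow-up visits will be described as shown in" the overall quality-of-life shell, and sends the stratified results to the shells that follow it. In SAP Annex 2 that shell (Table Shell 46) has the column headings "12 months 18 months 24 months 30 months 36 months". The same five headings stand on Table Shells 47.1, 48.1, 49.1, 50.1, 51.1, 52.1 and 53.1. The companion shells that are not printed are covered by the line "The same format will be used to". SAP 6.2 defines no other quality-of-life output: no change from baseline and no longitudinal summary.

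**The concern.** The assessment times in the tables are not the times at which the form is collected. The first year is the most densely sampled period, and all of it before month 12 has no column. That includes the only pre-treatment measurement. Two columns are reserved for times that no patient can reach.

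Quality of life is a secondary objective in both documents. Forms are collected only while the patient is on palbociclib, so a patient who stops before the month-12 assessment contributes no score to any table. Tables that start at month 12 describe only patients who have stayed on drug for about a year, who are likely to be those tolerating it and benefiting from it. Without a baseline column the reader cannot make even an informal before-and-during comparison.

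**Working it through.** **1. Scheduled times from the documents' own rules.** Baseline is 0. Every 3 months through year one gives 3, 6, 9 and 12. Every 6 months up to the 24-month limit gives 18 and 24. The documents do not print this list, but it follows from the stated intervals and the cap.

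**2. Comparison with the shell columns.**

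| | Months | Count |
|---|---|---|
| Scheduled | 0, 3, 6, 9, 12, 18, 24 | 7 |
| Shell columns | 12, 18, 24, 30, 36 | 5 |
| In both | 12, 18, 24 | 3 |
| Collected, no column | 0, 3, 6, 9 | 4 of 7 |
| Column, no possible data | 30, 36 | 2 of 5 |

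**3. Could a window or a longer follow-up explain the headings?** The month-24 window closes at 24 + 28/30.4375 = 24.9 months. A month-30 window of the same width would open at 30 − 28/30.4375 = 29.1 months. They do not meet. If follow-up ran to 36 months, the last two columns could be filled, but baseline and months 3, 6 and 9 would still be absent. No reading of the schedule reproduces the shells.

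**4. Illustrative size.** The documents give no expected time on drug. I assume 200 patients (protocol 8.1), full completion, and time on palbociclib following progression-free figures cited in protocol 6.1.

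*Scenario A: first-line palbociclib plus letrozole, progression-free 92.7%, 75.5% and 51.6% at 6, 12 and 18 months.* Months 3 and 9 are interpolated geometrically: 200 × √0.927 = 193 and 200 × √(0.927 × 0.755) = 167. Month 24 carries the month 12-to-18 ratio forward: 200 × 0.516 × (0.516/0.755) = about 70.

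*Scenario B: palbociclib plus aromatase inhibitor, 84.1% at 12 months, constant hazard.* Expected forms at month t are 200 × 0.841^(t/12).

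*Scenario C: palbociclib plus fulvestrant, median PFS 9.5 months, constant hazard.* Expected forms at month t are 200 × 0.5^(t/9.5).

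| Month | 0 | 3 | 6 | 9 | 12 | 18 | 24 | Total | Months 12+18+24 | Share tabulated |
|---|---|---|---|---|---|---|---|---|---|---|
| A | 200 | 193 | 185 | 167 | 151 | 103 | 70 | 1,070 | 325 | 30% |
| B | 200 | 192 | 183 | 176 | 168 | 154 | 141 | 1,214 | 464 | 38% |
| C | 200 | 161 | 129 | 104 | 83 | 54 | 35 | 765 | 172 | 22% |

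Totals are taken before rounding. Patients with no score in any table are those off drug by month 12: A, 200 − 151 = 49; B, 200 − 168 = 32; C, 200 − 83 = 117. Scenario C treats the whole cohort as if it had the fulvestrant figure, so it is an outer case and not a forecast.

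**The case against.** The best defence is that the loss is conditional. No SAP rule excludes early forms. SAP 6.2 speaks generally of follow-up visits, and Annex 1 gives the quality-of-life items the same general time point, which would cover months 3, 6 and 9. The shells carry other stale content: Shells 10 and 11 list Algeria and Kuwait and omit Jordan and Qatar. The headings may therefore be a leftover that a programmer would correct. This softens the word *unreported* but does not remove the conflict. SAP 6.2 ties the output to the shell, no shell has an earlier column, and visible errors elsewhere in the shells give no assurance that this one would be caught. The SAP was developed from protocol version 2.0, but the log for version 3.0 lists no change to the quality-of-life schedule, and the SAP itself states both the schedule and the 24-month limit.

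Second, a patient who stops early might still be counted in a Missing row, because the SAP does not define the denominator of that row or of the total. That stands. The supported statement is that such a patient contributes no score, not that the patient is necessarily absent from every count.

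Third, the form counts rest on a proxy. Patients stop palbociclib for reasons other than progression, completion will not be full, and the cohort mixes lines and partners. That also stands. The percentages illustrate the effect and do not bound it.

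Finally, the objective is descriptive and secondary with no testing, which limits how serious this can be.

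**Conclusion.** The concern holds. The SAP's quality-of-life shells contradict both the protocol's collection schedule and the SAP's own text. Followed as written, 4 of the 7 scheduled assessments, including baseline, are never tabulated, and 2 of the 5 columns cannot be filled. These counts need no assumption beyond the stated intervals and the 24-month limit. The secondary quality-of-life objective would then be described only for patients on drug at about one year.

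The share of forms that reach a table is about 30% or 38% in the two aromatase-inhibitor scenarios and lower under the fulvestrant figure. All of these depend on full completion and on progression-free rates standing in for time on treatment. The point should be corrected before the tables are programmed. It does not touch the primary objectives.

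**What to change.** In SAP Annex 2, Table Shells 46 to 53, replace the column headings with baseline, 3, 6, 9, 12, 18 and 24 months, and delete 30 and 36 months. In Annex 1, change the time point of the quality-of-life items to match, with baseline named.

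Three small points belong in the same edit:

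- State that a form is assigned to a column by the protocol windows (2 weeks either side in year one, 4 weeks after that), and restore the number missing from the year-one window in SAP Table 1, footnote 8.
- Define the denominators of the total and missing rows, so that patients who have stopped palbociclib are distinguished from those on drug with no form.
- Align the shell numbers: the overall quality-of-life table is Shell 47 in SAP 6.2, 45 in the list of shells and 46 in Annex 2.

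The cost is SAP wording and table layout. No new data, visits or patient burden arise, because the forms are already scheduled.
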